1.2.3 Pharmacokinetic Studies

1.2.3.1 Pharmacokinetic study of single intravenous injection of pralopiracetam and palonosetron in rhesus monkeys

After intravenous administration of HRS5580 to rhesus monkeys, the parent drug HRS5580 rapidly converts to its active metabolite rolapitacetam in plasma. HRS5580 is eliminated from plasma quickly with a half-life of only 0.16 hours, and no detectable parent drug remains in plasma 2 hours post-donation, with rolapitacetam being the predominant metabolite. The parent drug exposure is approximately equivalent to 1.7% of rolapitacetam. Following HRS5580 administration, plasma rolapitacetam exposure levels approach those observed after equivalent molar doses of rolapitacetam hydrochloride, with an AUC ratio of 98.9%. After intravenous administration of fosforolapitacetam palonosetron to rhesus monkeys, HRS5580 rapidly converts to rolapitacetam in plasma, with a half-life of only 0.13 hours. HRS5580 is undetectable in plasma 2 hours post-donation, and its AUC is approximately equivalent to 2% of rolapitacetam. Plasma exposures of HRS5580 and rolapitacetam were 115% and 100.2% of those observed in the HRS5580-treated group, respectively.

The plasma exposure of rolapipitan was 99.1% of that of the isomolar dose of rolapipitan hydrochloride injectable emulsion. Following a single intravenous injection of fosforylated rolapipitan palonosetron, the plasma exposure of palonosetron was 80.7% of that observed with a single dose of palonosetron monotherapy.

1.2.3.2 Study on tissue distribution of single intravenous injection of HRS5580 in SD rats

After a single intravenous injection of 20 mg/kg HRS5580 in SD rats, only low concentrations of the parent drug were detected in tissues collected at 10 minutes post-administration. The majority of tissues exhibited concentrations below 1% of plasma levels, with rolapitamab being the predominant drug in tissues. Rolapitamab was primarily distributed in the lungs, adrenal glands, liver, pancreas, ovaries, adipose tissue, kidneys, spleen, and heart, with tissue concentrations consistently exceeding plasma levels and tissue exposure exceeding plasma exposure by approximately 10-fold. Brain tissue exposure was approximately 4.7 times higher than plasma exposure, indicating its ability to cross the blood-brain barrier. The concentration ratio of rolapitamab in whole blood to plasma was 0.95, suggesting its entry into red blood cells. Tissue exposure of rolapitamab in female rats was approximately three times that observed in male rats. At equivalent molar doses, intravenous administration of HRS5580 in rats resulted in rolapitamab exposure levels in most tissues comparable to those observed after emulsion administration, with exposure ratio values ranging from 0.73 to 1.33.

1.2.3.3 Metabolic study of HRS5580 in an in vitro hepatocyte system

After incubation for 180 minutes in various hepatocyte metabolic systems, HRS5580 primarily undergoes amide hydrolysis metabolism to generate rolapitamab. The metabolic rate of HRS5580 is highly consistent across different hepatocyte species, with no significant interspecies differences observed. The metabolism of HRS5580 is mainly catalyzed by cytoplasmic enzymes containing free sulfhydryl groups and microsomal hydrolytic enzymes, with carboxylic esterases CES1 and CES2 playing a minor role in hydrolysis.

1.2.3.4 Metabolite Study of HRS5580 in Animals

HRS5580 undergoes extensive metabolism in rats, with 27 metabolites detected. The primary metabolic pathways include hydrolysis to form rolapipitan (M1), followed by further metabolic processes such as mono-oxidation (M2), dehydrogenation (M3), mono-oxidation coupled dehydrogenation (M4), and dual oxidation coupled dehydrogenation (M5), with the majority excreted via feces. In both rat and rhesus monkey plasma, the predominant metabolite is the hydrolyzed rolapipitan. Only trace amounts of the parent drug HRS5580 were detected in pooled blood samples collected within 2 hours after intravenous administration, while no HRS5580 was detected in urine or fecal samples.

2 Research Objectives

To evaluate the efficacy and safety of fosfoprolaplatin palonosetron for injection in preventing nausea and vomiting induced by multiple cycles of immunotherapy plus chemotherapy

in patients with esophageal cancer and lung cancer.

3 Study Design and Methods

This study is a randomized, parallel, cohort study designed to enroll 120 subjects, with 60 subjects per cohort. An interim analysis will be conducted when 40% of the subjects complete the study.

The trial consists of a screening phase, treatment phase, and safety follow-up phase. Pharmacotherapy is administered according to the trial protocol, followed by corresponding follow-up and examinations as specified in the trial schedule. During the study period, if the investigator determines that the subject indeed requires rescue antiemetic medication, rescue treatment may be provided based on clinical circumstances. The specific type, administration method, dosage, and frequency of the medication are determined by the investigator.

Study period: June 2025-September 2026

3.1 Selection Criteria

Participants must meet all the following inclusion criteria simultaneously during screening and randomization to be eligible for enrollment in this study:

- (1) Age ≥ 18 years, with no gender restriction;
- (2) Locally advanced/metastatic esophageal cancer and lung cancer confirmed by histology or cytology, and treated as first-line therapy;
- (3) Planned to receive at least 4 cycles of chemotherapy based on cisplatin and carboplatin combined with immunotherapy;
- (4) Expected survival duration ≥ 3 months;
- (5) Eastern Cooperative Oncology Group (ECOG) physical status score of 0 or 1;
- (6) Good organ function, meeting the following criteria:
 - a: Neutrophil count $\geq 1.5 \times 10^9/L$;
 - b: Hemoglobin ≥ 90 g/L;
 - c: Platelet count $\geq 100 \times 10^9/L$;
 - d: Total bilirubin $\leq 1.5 \times ULN$;
 - e: In patients without known liver metastases, aspartate aminotransferase (AST) $\leq 2.5 \times ULN$ and/or alanine aminotransferase (ALT) $\leq 2.5 \times ULN$ (for patients with liver metastases, the limit may be relaxed to $\leq 5 \times ULN$);
 - f: Serum creatinine $\leq 1.5 \times ULN$ or creatinine clearance rate ≥ 50 ml/min;
 - g: Electrocardiogram (ECG): QTc ≤ 450 ms (male), QTc ≤ 470 ms (female);

h: Echocardiography: LVEF (left ventricular ejection fraction) $\geq 50\%$;

(7) Female participants of reproductive age, as well as male participants whose partners are women of reproductive age, must have employed an effective contraceptive measure from the time of signing the informed consent form until 6 months after the last dose administration. Female participants of reproductive age must have a negative blood pregnancy test result within 72 hours prior to randomization and must not be in the lactation period.

(8) Clearly understand and voluntarily participate in this study, and sign the informed consent form personally.

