- (13) Accompanied by poorly controlled serous cavity effusions, including pleural effusion, ascites, and pericardial effusion (patients with controlled effusions stabilized for ≥ 2 weeks after treatment may be included);
- (14) History of severe cardiovascular disease within the preceding 3 months, including but not limited to acute myocardial infarction (AMI), unstable angina pectoris, significant valvular or pericardial disease, ventricular tachycardia, symptomatic chronic heart failure (New York Heart Association [NYHA] class II to IV), and history of severe cardiac conduction abnormalities (e.g., torsades de pointes).
- (15) Randomized prior coexisting poorly controlled hypertension (two consecutive resting systolic blood pressure ≥ 160 mmHg and/or diastolic blood pressure ≥ 100 mmHg);
- (16) Patients with concurrent active hepatitis B virus infection (HBV DNA ≥ 2000 IU/mL or 10^4 copies/mL), active hepatitis C virus infection (HCV-Ab positive with HCV-RNA \geq upper limit of normal), acquired immunodeficiency syndrome (AIDS) or positive HIV test results, or positive syphilis test results;
- (17) Concomitant diseases contraindicated for dexamethasone administration, such as active infections (e.g., pneumonia) or any uncontrolled conditions (e.g., diabetic ketoacidosis, gastrointestinal obstruction, etc.);
- (18) Known contraindications for NK-1 receptor antagonists, 5-HT₃ receptor antagonists, or dexamethasone;
- (19) Participation in other clinical trials within the preceding 30 days (based on the use of investigational drugs);
- (20) Subjects deemed by investigators to have other conditions unsuitable for participation in this study.

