3.6 Research Flowchart

3.7 Statistical Analysis

Count data were summarized using frequency and percentage. Measurement data were summarized using mean, standard deviation, median, maximum value, and minimum value. Statistical analysis was performed using SAS 9.4 software.

Population analysis

Full Analysis Set (FAS): Includes all enrolled subjects who received the investigational drug, with primary efficacy analysis based on FAS.

Safety Analysis Set (SS): Includes all enrolled subjects who received at least one dose of the study drug.

Efficacy Analysis

If a participant's assessment of vomiting episodes is missing on any day during the overall period, resulting in an inability to determine whether the participant has achieved complete remission, the participant is recorded as having incomplete remission.

Sensitivity analysis for primary estimation targets: The sensitivity analysis methodology is identical to that of the primary estimation method, with only differences in the missing value imputation rules. If a participant's assessment of vomiting episodes is missing on any day during the study period, complete remission is determined based on the available data from that participant.

If the subject's assessment of vomiting episodes is missing on any day within the extended delay period, resulting in an inability to determine whether the subject has achieved complete remission, the subject is recorded as having incomplete remission.

safety analysis

AEs will be coded using the MedDRA dictionary. The frequency and incidence of

treatment-emergent adverse events (TEAEs) will be summarized by grouping according to System Organ Classification (SOC), preferred terms, and severity. Outcomes such as vital signs, electrocardiogram (ECG), and other clinical laboratory tests will be summarized by relative changes from baseline. Additionally, abnormal clinical laboratory test results will be described in a separate table.

4 Sample Size Calculation

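### Inclusion criterion (6)e joins the AST and ALT limits with and/or, so read literally one enzyme within its limit qualifies a subject and the other has no ceiling

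*Protocol*

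**What the plan says.** Protocol section 3.1 opens with a rule for the whole list: "Participants must meet all the following inclusion criteria simultaneously during screening and randomization". Criterion (6) is introduced by "Good organ function, meeting the following criteria" and has lettered items a to h.

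Item e begins "In patients without known liver metastases, aspartate aminotransferase (AST"), gives 2.5 x ULN as the AST limit, and continues "and/or alanine aminotransferase (ALT") with the same 2.5 x ULN limit. A parenthesis then says "for patients with liver metastases, the limit may be relaxed to" 5 x ULN. It does not say which enzyme or enzymes it covers.

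The synopsis, under Admission criteria (6)e, has the same text with the same connector, so neither place corrects the other.

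**The concern.** Every lettered item under criterion (6) is a condition for entry. Item e names two laboratory values but joins them with a connector that either value can satisfy by itself. If AST is within its limit, the literal rule asks nothing of ALT, and the reverse. That sits badly with a heading that calls for good organ function, and it is unlikely to be the effect the authors wanted.

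Two things are at stake. First, a subject with a marked elevation of one transaminase could be randomised and go on to a planned course of at least four cycles without breaching the written rule. Second, approximately five centres have to apply the item. Given identical laboratory values, one could enrol and another refuse, and a monitor would have no text to decide whether an enrolment was a protocol deviation. Section 5.2 requires deviations to be compiled before database lock, so the question will have to be answered at some point.

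**Working it through.** No sample-size, power or error-rate figure is involved, and the plan gives no number to reproduce. The check is a logical one.

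**Inputs**, all from section 3.1 (6)e and the matching synopsis item:
- A: AST is at or below 2.5 x ULN.
- B: ALT is at or below 2.5 x ULN.
- Connector: and/or, that is, inclusive or.

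**Step 1. Truth table, no known liver metastases.**

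| AST within limit | ALT within limit | Item e as written (A or B) | Item e if both limits bind (A and B) |
|---|---|---|---|
| yes | yes | met | met |
| yes | no | met | not met |
| no | yes | met | not met |
| no | no | not met | not met |

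As written, 3 of 4 combinations pass; if both limits bind, 1 of 4 passes. These are counts of logical cases, not proportions of patients.

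**Step 2. Example.** AST 2.0 x ULN and ALT 8 x ULN, no liver metastases. A is true (2.0 ≤ 2.5) and B is false (8 > 2.5). A or B is true, so item e is met as written; A and B is false, so it would not be met if both limits applied. With liver metastases the limit becomes 5 x ULN: 2.0 ≤ 5 is true and 8 > 5, so the outcome is the same under each reading.

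**Step 3. Does the lead-in settle it?** The rule that all criteria must be met requires item e to be met. It does not say how the two parts inside item e combine.

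**Step 4. How does the protocol use its connectors elsewhere?**
- Item (6)f, the next line, uses a plain *or* for a real alternative (serum creatinine or creatinine clearance). Item e uses neither a plain *or* nor *and*.
- Exclusion (15) in section 3.2 joins systolic pressure to diastolic with "and/or diastolic blood pressure". There either value is enough to exclude, so the connector tightens entry. In an inclusion item, the same inclusive meaning loosens entry.

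**Step 5. Does anything else cap AST or ALT?**
- Item (6)d limits total bilirubin, which is a separate test.
- Exclusion (16) concerns viral hepatitis, HIV and syphilis, with no transaminase limit.
- Exclusion (17) concerns conditions that contraindicate dexamethasone.
- Exclusion (20), "Subjects deemed by investigators to have other conditions unsuitable for participation in this study", is discretion without a threshold.

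None bounds either enzyme. The gap in item e is not closed elsewhere.

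**The case against.** The best defence is that the permissive reading is not the only one. Item e stands under a good-organ-function heading within a list that must be met in full. Since item (6)f writes a plain *or* where alternatives are wanted, item e can be read as naming two tests that share one limit. The English is also visibly a rough translation, so the connector may not reflect the source text, though this cannot be checked here. Many sites may already apply both limits. All of this is fair, and it is why the point is put as a literal reading and not as a statement of what the sponsor intends. It does not remove the defect, because no sentence tells a site which reading governs.

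It is also fair that bilirubin, the hepatitis exclusions, the dexamethasone exclusion and investigator judgement narrow the route by which a subject with a very high single enzyme would enter. They narrow it without closing it.

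Three stronger readings are tempting, and the protocol does not support them.
- A reader might infer that the safety analysis is distorted, because section 3.7 says that "other clinical laboratory tests will be summarized by relative changes from baseline", so a fall from 8 to 4 x ULN would look like a 50% improvement. The same section plans a separate table of abnormal laboratory results, in which such a value can still be shown. Section 8.1 counts worsening of pre-existing conditions, including laboratory findings, as an adverse event. The fall would also be a true description of that subject, and a subject who entered validly at 5 x ULN with liver metastases would be summarised in the same way. The connector does not cause this.
- A reader might take the item to mean that one *normal* enzyme is enough. The text asks only that the enzyme be within 2.5 x ULN, or 5 x ULN with liver metastases.
- A reader might want to express the effect as a share of an arm. The protocol gives no basis for estimating how many such subjects would enter.

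**Conclusion.** The criterion is wrong as written. Followed literally, item (6)e is met by one within-limit enzyme and leaves the other without an upper bound, contrary to its own heading; the liver-metastasis clause inherits the fault. The consequences are possible randomisation of subjects with a marked rise in one transaminase, possible differences between centres on the same values, and no clear basis for classing such an enrolment as a deviation.

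The reach is limited. The primary endpoint, the sample size and every stated figure are untouched. The full analysis set in section 3.7 takes in all enrolled subjects who received the investigational drug, so its definition does not turn on this item. The number of subjects concerned is unknown.

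The conclusion rests on reading and/or as inclusive or, which is its ordinary sense and fits its use in exclusion (15), and on the absence of any other transaminase limit in the protocol. That centres would actually diverge is a possibility the text leaves open, not something it shows. Whether the thresholds themselves are suitable is not judged here.

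**What to change.** In section 3.1 (6)e and in the synopsis, reconcile the connector with the stated purpose of the criterion:
- say that the existing 2.5 x ULN limit applies to each of AST and ALT in patients without known liver metastases;
- say that the existing 5 x ULN limit applies to each of AST and ALT in patients with liver metastases.

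All thresholds stay as they are.

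The drafting cost is a few words in two places. The sponsor's statement at the front of the protocol ties implementation of a revised protocol to ethics committee approval, so there is a small administrative cost as well. The current version is dated January 14, 2026, within a study period of June 2025 to September 2026, so the change would probably come mid-study and bind only later entrants. A few candidates with one enzyme above the limit, whom a centre might otherwise have accepted, could become ineligible.

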3.2 Exclusion Criteria

Participants who meet any of the following criteria during screening and randomization are ineligible to participate in this study:

(1) Received or planned to receive abdominal (including diaphragmatic plane and below) or pelvic radiotherapy within the previous 7 days prior to randomization, or during days 1 to 8 of treatment;

(2) Schedule administration of highly emetogenic chemotherapy agents within days 2 to 8 after platinum infusion;

(3) Planned to receive chemotherapy regimens including conventional paclitaxel (using castor oil as solvent);

(4) Randomly administer drugs with potential antiemetic effects within the preceding 2 days: first-generation 5-HT₃ receptor antagonists (e.g., ondansetron), phenothiazines (e.g., prochlorazine), butyrophenones (e.g., haloperidol), benzamide derivatives (e.g., metoclopramide), domperidone, cannabinoids, traditional Chinese medicines with potential antiemetic effects, scopolamine, and cecirizine.

(5) Had started treatment with benzodiazepines or opioid preparations within the preceding 2 days (excluding triazolam, temazepam, or midazolam taken alone daily);

(6) Subjects who began morphine use within the preceding 7 days (excluding those on stable dosage regimens);

(7) Received systemic corticosteroid therapy (including but not limited to dexamethasone, hydrocortisone, methylprednisolone, or prednisolone) or sedative antihistamines (such as diphenhydramine) within the preceding 7 days (Note: Single-dose steroid administration for contrast agent allergy prophylaxis and topical or inhaled administration are permitted), except for cases requiring hormone pretreatment on the day before chemotherapy.

(8) Palonosetron use within the preceding 14 days;

(9) Use of NK-1 receptor antagonists within the preceding 28 days;

(10) Use of specific CYP3A4 substrates (terfenadine, cisapride, astemizole) or CYP3A4 inhibitors (e.g., ritonavir, clarithromycin, ketoconazole or itraconazole, diltiazem) within 7 days prior to randomization, or use of CYP3A4 strong inducers (e.g., phenobarbital, rifampin, phenytoin, carbamazepine) or specific CYP2D6 substrates (thiuridazine, pimozide) within 28 days prior to randomization;

- (11) Vomiting and/or retching, nausea occurring within the preceding 24 hours;
- (12) Subjects with symptomatic brain metastases;
- (13) Accompanied by poorly controlled serous cavity effusions, including pleural effusion, ascites, and pericardial effusion (patients with controlled effusions stabilized for ≥ 2 weeks after treatment may be included);
- (14) History of severe cardiovascular disease within the preceding 3 months, including but not limited to acute myocardial infarction (AMI), unstable angina pectoris, significant valvular or pericardial disease, ventricular tachycardia, symptomatic chronic heart failure (New York Heart Association [NYHA] class II to IV), and history of severe cardiac conduction abnormalities (e.g., torsades de pointes).
- (15) Randomized prior coexisting poorly controlled hypertension (two consecutive resting systolic blood pressure ≥ 160 mmHg and/or diastolic blood pressure ≥ 100 mmHg);
- (16) Patients with concurrent active hepatitis B virus infection (HBV DNA ≥ 2000 IU/mL or 10^4 copies/mL), active hepatitis C virus infection (HCV-Ab positive with HCV-RNA \geq upper limit of normal), acquired immunodeficiency syndrome (AIDS) or positive HIV test results, or positive syphilis test results;
- (17) Concomitant diseases contraindicated for dexamethasone administration, such as active infections (e.g., pneumonia) or any uncontrolled conditions (e.g., diabetic ketoacidosis, gastrointestinal obstruction, etc.);
- (18) Known contraindications for NK-1 receptor antagonists, 5-HT₃ receptor antagonists, or dexamethasone;
- (19) Participation in other clinical trials within the preceding 30 days (based on the use of investigational drugs);
- (20) Subjects deemed by investigators to have other conditions unsuitable for participation in this study.

3.3 Exit Criteria

Participants may voluntarily withdraw from the trial at any time, or be required to withdraw by investigators due to safety concerns, behavioral reasons, or inability to comply with protocol-specified study visit schedules or procedures at their respective research centers.

Reasons for leaving the study may include:

- The subject voluntarily withdrew and declined further follow-up;
- lost to follow-up;
- die ;
- The sponsor terminated the study prematurely.

If a participant fails to return to the center for follow-up as scheduled, every effort should be made to contact the participant. The investigator should inquire about the reason for withdrawal

and request the participant to return to the center for a withdrawal visit, during which any unresolved adverse events (AEs) should be followed up, if applicable. If the participant refuses to attend further visits at the research center, continued tracking and collection of relevant information should be maintained unless the participant voluntarily withdraws. In such cases, no further study evaluations should be conducted, and no additional data should be collected.

